7.1.2 Contraception

Subjects at risk for pregnancy should be using a contraceptive method during screening phase. However, during the Treatment Phase, subjects are not required to use a contraceptive other than the LNG20 IUS. Any method of contraception may not prevent pregnancy. LNG20 IUS is currently FDA-approved for contraception for up to 6 years of use. [REDACTED]

[REDACTED]

[REDACTED]

[REDACTED]

[REDACTED]

[REDACTED]

[REDACTED]

[REDACTED]

■	■■■	■■■■	■■■■■	■■■■■■	■■■■■■■
■	■■■	■■■	■■■■	■■■■■	■■■■■■
■	■■■	■■■	■■■■	■■■■■	■■■■■■
■	■■■	■■■	■■■■	■■■■■	■■■■■■
■	■■■	■■■	■■■■	■■■■■	■■■■■■
■	■■■	■■■	■■■■	■■■■■	■■■■■■
■	■■■	■■■	■■■■	■■■■■	■■■■■■

7.1.3 Pregnancy

If pregnancy occurs during study treatment, the subject will be instructed that the LNG20 IUS should be removed in accordance with standard medical care. The investigator will discuss with the subject all pregnancy options and will provide information regarding providers and health care facilities. Pregnancy management is outlined in Appendix F.

All pregnancies that occur while a subject is using the study IUS will be followed to completion. Pregnancy outcomes, including normal births, septic abortions, ectopic pregnancies, birth defects, and premature deliveries, whenever this information can be obtained for all women who get pregnant during the study.

7.1.3.1 Miscarriage

Women who become pregnant and miscarry while using an LNG IUS are rarely reported in the literature. The overall number of reports is too low to understand whether the risk is the same or different than the risk of spontaneous abortion in the general population of pregnant women. Of 15 confirmed pregnancies reported by Backman et al., 2004 that occurred with the LNG 52 mg IUS *in situ*, 8 (53%, 95% CI 28, 79%) ended in miscarriage. Of the 5 pregnancies reported by Andersson et al., 1994, 2 (40%, 95% CI 0, 83%) ended in miscarriage. One of these women became pregnant with the LNG IUS *in situ* and the other became pregnant after an unrecognized

expulsion. [REDACTED]

[REDACTED]

7.1.3.2 Ectopic Pregnancy

Women who become pregnant while using an LNG IUS can experience an ectopic (extrauterine) pregnancy. Overall, the risk of a woman having an ectopic pregnancy is lower than the general population because the risk of pregnancy is significantly decreased. [REDACTED]

[REDACTED]

[REDACTED]

[REDACTED]

[REDACTED]

7.1.3.3 Effects on gestation and offspring

When pregnancy continues with the LNG20 IUS in place, the risks of long-term effects on the offspring are unknown. Based on data from copper IUDs, pregnancies that continue are at an increased risk of pre-term (<37 weeks) delivery as compared to women who conceive without an IUD in place (Ganer et al., 2009). The risk is highest if the IUD is not removed (18%) as compared to if the IUD is removed (14%); the risk in the general population is around 7%. Additionally, pregnancies that continue are also at a higher risk of being complicated by chorioamnionitis; 7% if the IUD remains, 4% if the IUD is removed, and slightly less than 1% in the general population (Ganer et al., 2009). It is unknown whether these risks are similar for women who conceive while using a LNG IUS.

7.1.4 Difficult Insertion/Removal

[REDACTED]
[REDACTED]

Management of difficult insertion and removal are outlined in Appendix G.

7.1.5 Expulsion

[REDACTED]
The expulsion rate in the first year in women using a LNG 52 mg IUS for HMB is approximately the same (3.9%) (Mawet et al., 2014). Expulsion management is outlined in Appendix G.

7.1.6 Pelvic Infection

[REDACTED]
[REDACTED]
[REDACTED]
[REDACTED] Pelvic infection management is outlined in Appendix G.

7.1.7 Perforation

The incidence of uterine perforation during a LNG20 IUS placement attempt in the M360-L102 study is 0.1% (Eisenberg et al., 2015). Perforation management is outlined in Appendix G.

7.1.8 Pelvic/Abdominal Pain

Some women experience pelvic pain or cramping with insertion and a small percentage notice continued or intermittent pain with continued use of LNG20 IUS. Pain may be due to uterine cramping (perhaps related to placement or the presence of the IUS) or functional ovarian cysts. However, there is no clear data on whether the incidence of functional ovarian cysts is increased in LNG20 IUS users as compared to the general population. In the M360-L102, ovarian cysts over multiple years of use are reported in 4.5% of women and discontinuation for ovarian functional cysts occurred in only 0.3% (Teal et al., 2019).

7.1.9 Systemic Side Effects

Although systemic levonorgestrel levels are very low, women using LNG20 IUS do report progestin-related side effects, albeit at low rates. Use of a LNG IUS may affect glucose tolerance; subjects with diabetes should continue routine monitoring of blood glucose concentration with their diabetes care provider.

7.1.10 Mortality

The risk of death with IUD use ranges from 1 to 6 per million users per year. This rate is lower than all other female methods of contraception and lower than use of no contraception when considering the risk of pregnancy (Harlap et al., 1991).

7.1.11 Missing Strings

Rarely, the IUS strings may not be visible during a speculum examination. The IUS is most typically in the uterus when strings are missing. However, the strings could be missing because of a perforation or expulsion. Missing string management, including appropriate imaging to determine the location of the IUS, is outlined in Appendix G.

7.1.12 Phlebotomy

There is an infrequent chance of pain, bruising, or bleeding at the site of the needle puncture, and a rare chance of fainting, inflammation of the vein, or infection.

7.1.13 Pelvic Examination

The subject may infrequently experience some discomfort during the pelvic exams, Pap test, and Chlamydia and gonorrhea testing. Any reaction would most likely include redness, itching, irritation, or vulvovaginal discomfort. Infrequently the subject may have a small amount of vaginal bleeding after a Pap test, Chlamydia or gonorrhea testing.

7.1.14 Endometrial Biopsy

An endometrial biopsy commonly causes light bleeding the day of the procedure and uterine/pelvic cramping for a few minutes, primarily during the procedure. Rarely, a biopsy can result in infection or uterine perforation.

7.1.15 Vaginal Ultrasound

A formal vaginal ultrasound examination will be performed for women at screening (if not performed within the last 6 months), if a subject has missing IUS strings, if a subject becomes pregnant, and for other indications that would clinically require such an examination. Typically, the subject may feel mild discomfort similar to a pelvic examination.

7.1.16 Local Anesthesia

If the clinician uses cervical anesthesia during insertion or removal, there is an infrequent risk of the subject experiencing an unusual taste in her mouth, ringing in her ears, nausea or light-headedness. Rarely, a seizure or death can occur.

7.1.17 Emotional Discomfort

Some of the questions asked in this study may make the subject feel uncomfortable or embarrassed. A subject can refuse to answer any question that causes emotional discomfort, from any person, at any time.

7.2 Overall Assessment of Benefits and Risks

All available information supports a favorable risk-benefit ratio.

7.3 General Plan to Manage Safety

The safety profile of currently available IUSs, as reported during clinical trials and since marketing approval, has been well-characterized. Adverse events that have been reported in relation to IUS use, such as expulsion, vaginal bleeding, uterus perforation, and infection will be specifically monitored. Serious Adverse Events will be reported as per FDA guidance.

7.4 Pregnancy Assessment and Reporting

High sensitivity urine pregnancy tests are performed at each study visit. For any positive pregnancy test on IUS treatment through Visit 8/Early Discontinuation:

- Immediately obtain a serum quantitative hCG
- Within 3 calendar days conduct a transvaginal ultrasound for pregnancy confirmation, pregnancy location and date of conception
 - If the pregnancy is too early for ultrasound verification have the subject return in approximately 1-2 weeks for an unscheduled visit and repeat ultrasound examination
- Complete a Pregnancy Narrative (See Study Reference Manual)

If the subject reports a positive pregnancy test on her own (performed at home) she should be seen as soon as possible for a high-sensitivity urine pregnancy test to be performed at the clinic and if the test is positive perform the required procedures above.

For pregnancies occurring before IUS discontinuation, ultrasonography will also be used to verify presence of the IUS in the uterus.

All confirmed pregnancies occurring during study treatment will be followed to completion.

Pregnancy outcomes, including normal births, septic abortions, ectopic pregnancies, birth defects, and premature deliveries, whenever this information is available, will be obtained. Pregnancy reporting should include a Pregnancy Report Form Case Report Form (CRF) and Pregnancy Outcome CRF.

Pregnancy management is outlined in Appendix F.

7.5 Adverse Events Assessments

During the study, the Investigator or study site personnel will be responsible for querying and recording adverse events (AEs) and serious adverse events (SAEs), as detailed below. For the Sponsor to fulfill safety assessment obligations the Investigator should report all SAEs resulting from study participation (e.g., complications resulting from a study-required procedure, such as the taking of a blood sample).

7.6 Definition of an Adverse Event

An **adverse event** is any untoward medical occurrence in a patient or clinical investigation subject administered a pharmaceutical product and which does not necessarily have to have a causal relationship with this treatment. An AE can therefore be any unfavorable and unintended sign (that could include a clinically significant abnormal laboratory finding), symptom, or disease temporally associated with the use of a medicinal product, whether or not considered related to the medicinal product. The Investigator should attempt to establish a diagnosis of the event based on signs, symptoms, and/or other clinical information. In such cases, the diagnosis should be documented as the AE/SAE and not the individual signs/symptoms.

- Any medical condition or clinically significant laboratory abnormality with an onset before the study IUS insertion is considered to be pre-existing and should not be documented in the CRF as an AE, but should be recorded as medical history.
- Any AE (i.e., a new event or an exacerbation of a pre-existing condition) with an onset from the beginning of study IUS insertion through Visit 8/Early Discontinuation and the post-Treatment Phase safety contact (if applicable) should be recorded.
- All AEs must be recorded regardless of the severity or relationship to study medication.
- All AEs that result in permanent discontinuation of the investigational product must be reported, whether serious or non-serious.
- An AE **does** include:
 - exacerbation of a pre-existing illness
 - increase in frequency or intensity of a pre-existing episodic event or condition
 - condition occurring after study IUS insertion
 - continuous persistent disease or symptoms present at baseline that worsen following the start of the study
- An AE **does not** include:
 - medical or surgical procedures (e.g., surgery, endoscopy, tooth extraction, transfusion); the condition that leads to the procedure may be an adverse event if the condition has worsened since enrolling in the study

- pre-existing diseases or conditions present or detected prior to start of study drug administration that do not worsen
- situations where an untoward medical occurrence has not occurred (e.g., hospitalization for elective surgery, social and/or convenience admissions)
- disease or disorder being studied or sign or symptom associated with that disease
- overdose of concomitant medication without any signs or symptoms

7.7 Definition of a Serious Adverse Event

A **serious adverse event (SAE)** is any adverse event occurring within the timelines specified in the protocol that results in any of the following outcomes:

- Death
- Life-threatening situation
 - The subject was at immediate risk of death from the event as it occurred
 - Does not include an event that might have led to death, if it had occurred with greater severity
- Inpatient hospitalization or prolongation of existing hospitalization
 - Does not require inclusion of elective surgery; however, any adverse event occurring during that hospitalization that prolongs the hospital stay would be an SAE
 - Does not have a requirement to be greater than a twenty-four hour stay; if the subject was admitted to the hospital for less than a day for treatment or observation, the definition of “Inpatient hospitalization” is met
 - Treatment in an outpatient clinic or Emergency department does not constitute “inpatient hospitalization”
 - Complications that occur during hospitalizations are AEs; if a complication prolongs hospitalization, it is an SAE
- Persistent or significant disability/incapacity
- Congenital anomaly/birth defect in the offspring of a subject who received study drug
- Important medical events that may not result in death, be immediately life-threatening, or require hospitalization, may be considered an SAE when, based upon appropriate medical

judgment, they may jeopardize the subject and may require medical or surgical intervention to prevent one of the outcomes listed in this definition. Examples of such events are intensive treatment in an emergency room or at home for allergic bronchospasm; blood dyscrasias, or convulsions that do not result in hospitalization; or development of drug dependency or drug abuse.

7.8 Prompt Reporting of SAEs to Sponsor

The Sponsor has requirements for reporting serious adverse events to regulatory agencies for a drug under clinical investigation. The Sponsor must be notified within **24 hours of discovery** and the Investigator determines that an adverse event meets the protocol definition of an SAE. Any fatal or life-threatening events should be reported immediately by telephone to the Sponsor. All SAEs occurring from the beginning of study screening through Visit 8/Early Discontinuation and the post-Treatment Phase safety contact (if applicable) require reporting to the Sponsor. Investigators should not wait to receive additional information to fully document the event prior to notifying the Sponsor but should provide as much relevant information as immediately available. Further details of the event can be provided as they become available. The procedures for reporting SAEs are in the Study Reference Manual.

- It is very important that the Investigator provides an assessment of the causal relationship between the event and the study drug at the time of the initial report (see 7.10.2 for Causality definitions)
- The Investigator, or responsible person according to local requirements, must comply with the applicable local regulatory requirements concerning the reporting of SAEs to regulatory authorities and the IRB

7.9 Clinical Laboratory Abnormalities and Other Abnormal Assessments as Adverse Events and Serious Adverse Events

Abnormal laboratory findings (e.g., clinical chemistry, hematology) or other abnormal assessments (e.g., X-rays, vital signs) per se are not reported as AEs. However, abnormal findings that are deemed **clinically significant** (i.e., associated with signs and/or symptoms or requiring therapeutic intervention) must be recorded as AEs if they meet the definition of an

adverse event (and recorded as an SAE if they meet the criteria of being serious) as described previously. Clinically significant abnormal laboratory or other abnormal findings that are detected after IUS insertion or that are present at baseline and worsen following study IUS insertion are included as AEs (and SAEs if serious).

The Investigator should exercise his or her medical judgment in deciding whether an abnormal laboratory finding or other abnormal assessment is clinically significant. A clinically significant laboratory abnormality in the absence of clinical symptoms may also jeopardize the subject and may require intervention to prevent immediate consequences (e.g., a markedly high serum potassium concentration may not be accompanied by arrhythmia, yet be of a magnitude to require potassium-binding resin administration to prevent such sequelae). Subjects should undergo repeat testing of clinically significant abnormal laboratory findings as soon as they are recognized.

7.10 Reporting of Adverse Events

Any AE with an onset after study IUS insertion or until the final safety contact after study discontinuation must be documented in the subject's study records and appropriate CRF.

7.10.1 Adverse Event CRFs

Specific Adverse Events are recorded on different CRFs.

AEs related to bleeding or cramping/pain

- With insertion - report on the IUS Insertion Questionnaire CRF
- With removal - report on the IUS Removal Questionnaire CRF
- During IUS use
 - The subject's diary acts as the menstrual bleeding or cramping/pain AE CRF
 - Menstrual bleeding or cramping/pain should also be reported on the general AE CRF only if:
 - Bleeding or cramping/pain are not related to the IUS or a menstrual condition

- Bleeding or cramping/pain meet serious criteria; an SAE report would also have to be submitted (this exception is due to data system requirements)
- Bleeding or cramping/pain result in the IUS being removed (this exception is due to data system requirements)
- Bleeding and cramping event terminology-consistent use of adverse event terminology is essential for characterization of the product:
 - Heavy menstrual bleeding (increase in flow worse than baseline)
 - Irregular bleeding (variation in bleeding pattern)
 - Infrequent bleeding (bleeding episodes that are too rare)
 - Amenorrhea (no bleeding or spotting)
 - Frequent bleeding (too many bleeding/spotting episodes)
 - Prolonged bleeding (persistent bleeding/spotting)

7.10.2 Causality Assessment: Adverse Event Relationship

The Investigator's causality assessment should consider the potential etiologies for the observed adverse event. An adverse event may be related to the study drug, other concomitant medications, the underlying disease pathology, intercurrent illness, a procedure performed in the course of the study, or another reason. Among the potential etiologies, the Investigator should make a determination based on the most likely causal relationship. When a causality assessment is provided for a serious adverse event, it is important to include a rationale for the assessment so that a better understanding of the reported event can be compiled. The rationale should be accompanied by all available supporting evidence, including relevant laboratory tests, histopathology evaluations and the results of other diagnostic procedures. The Investigator's rationale with supporting evidence is valuable when the Sponsor performs a cumulative analysis of similar events.

The Investigator will assess the relationship of the AE to the study IUS or the IUS insertion or removal procedures by using the following general guidelines:

- **Not Related:** A causal relationship between the study IUS/procedures and the AE can be ruled out (e.g., based on the temporal sequence, absence of a reasonable pathophysiological mechanism, or direct evidence of actual cause).
- **Unlikely related:** A clinical event, including a laboratory test abnormality, with a temporal relationship to IUS insertion or the onset of an IUS insertion or removal procedure which makes a causal relationship improbable, and in which other drugs, chemicals or underlying disease provide plausible explanations.
- **Probably Related:** A clinical event, including a laboratory test abnormality, with a reasonable time sequence to IUS insertion or the onset of an IUS insertion or removal procedure, unlikely to be explained by concurrent disease or other drugs or chemicals. Information on drug withdrawal may be lacking or unclear.
- **Related:** A clinical event, including a laboratory test abnormality, with a reasonable time sequence to IUS insertion or the onset of an IUS insertion or removal procedure, cannot be attributed to concurrent disease or other drugs or chemicals, and which follows a clinically reasonable response on withdrawal.

7.10.3 Adverse Event Severity

The Investigator will assess the severity of the AE using the following general guidelines:

- **Mild:** An AE that is usually transient, requiring no special treatment, and does not interfere with the subject's daily activities
- **Moderate:** An AE that introduces a low level of inconvenience or concern to the subject and may interfere with daily activities, but is usually ameliorated by simple therapeutic measures
- **Severe:** An AE that interrupts a subject's usually daily activity and typically requires systemic drug therapy or other treatment (a severe AE may not necessarily qualify as a SAE)
- **Life-threatening:** An AE that put the subject at immediate risk of death from the event as it occurred. This does not include an event that might have led to death if it had occurred with greater severity.

7.10.4 Adverse Event Outcome

The Investigator will categorize the outcome of each Adverse Event according to the definitions below:

- **Resolved:** The subject recovered from the AE
- **Resolved with sequelae / Stable:** A condition whereby the consequences of a disease or injury include lingering effects that are not worsening
- **Ongoing:** At the time of the last assessment, the event is ongoing, with an undetermined outcome. Note: Ongoing AEs are not considered resolved as a result of death and no AE stop date should be recorded for an AE that is ongoing at the time of death.
- **Fatal:** Adverse Event directly caused death. The Sponsor may request that the Investigator perform or arrange for the conduct of supplemental measurements and/or evaluations. If a subject dies during participation in the study or during a recognized follow-up period, the Sponsor should be provided with a copy of any post-mortem findings, including histopathology.
- **Unknown:** The outcome is not known and cannot otherwise be categorized (e.g., subject became lost to follow-up (LTFU) or withdrew consent)

The Investigator should attempt to establish a diagnosis of the event based on the signs, symptoms and/or other clinical information. In such cases, the diagnosis should be documented as the AE (and SAE if serious) and not the individual signs/symptoms.

In the case of abnormal labs or diagnostic tests judged to be clinically significant by the Investigator a diagnosis, if known, or clinical signs or symptoms if the diagnosis is unknown, rather than the clinically significant laboratory finding or abnormal assessment, should be used to complete the AE/SAE page. If no diagnosis is known and clinical signs or symptoms are not present, then the abnormal finding should be recorded on the AE/SAE page. If an SAE report is completed, pertinent laboratory data should be recorded on the SAE form, preferably with baseline values and copies of laboratory reports.

7.11 Clarification of Action Taken with IUS

The Investigator will categorize the Action Taken with IUS according to the definitions below:

- **None:** The IUS was not removed as result of the Adverse Event

- IUS was left in place
- IUS was removed at the time of the AE but due to:
 - A different AE
 - A different reason
 - The subject wanting the IUS removed because of the AE despite the investigator stating the AE was not a reason to have the IUS removed
- IUS was already removed prior to the AE start date
- AE was a full expulsion
- subject was LTFU or withdrew consent prior to IUS removal
- **IUS Removed for Non-Safety Reasons:** The IUS was removed for an Adverse Event even though the IUS could have remained in place without placing the subject at immediate risk for a serious complication related to the IUS
- **IUS Removed for Safety Reasons:** The IUS was removed for an Adverse Event because the subject was at immediate risk for a serious complication as a direct result of the AE if the IUS had not been removed
- **Unknown:** The IUS was removed by another provider

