Hemoglobin and ferritin values increase with LNG 52 mg IUS use in women with HMB. In a randomized study assessing the efficacy of a LNG IUS and oral MPA (10 mg/day for 10 days) in women with confirmed HMB, hemoglobin and serum ferritin levels were assessed at baseline, and at Cycles 3 and 6 of treatment. Baseline median hemoglobin and ferritin levels were 12.4 g/dL and 19.0 mcg/L with the LNG IUS and 12.2 g/dL and 19.0 mcg/L with oral MPA, respectively. At Cycle 6, the corresponding medians were 13.4 g/dL and 34.0 mcg/L with the LNG IUS and 12.6 g/dL and 21.0 mcg/L with oral MPA (Kaunitz et al., 2010). The increases from baseline to Cycle 6 were greater in the LNG IUS group than in the oral MPA group for hemoglobin levels (7.5% vs. 1.9%; $p < .001$) and median serum ferritin levels (68.8% vs. 14.3%; $p < .001$).

Of note, amenorrhea rates in women who use the LNG 52 mg IUS for HMB are lower than the rates reported in women who use the LNG 52 mg IUS primarily for contraception. In contracepting women, approximately 20% of women are amenorrheic for a period of 90 days or more by the end of the first year of use (Andersson et al., 1994, Schreiber et al., 2018); this amenorrhea rate is reached within about 9 months of use (Schreiber et al., 2018). Pooled data from four randomized trials comparing the levonorgestrel 52 mg IUS to medroxyprogesterone acetate orally, tranexamic acid orally, mefenamic acid orally and endometrial resection in 163 women with HMB demonstrates the change in bleeding seen in this specific population (Jensen et al., 2013). Amenorrhea rates in this population were 2% at 6 months and 9% at one year. By one year, an additional 24% were reporting infrequent bleeding/spotting. Only 6% of women using the LNG 52 mg IUS for HMB in these trials discontinued for bleeding complaints.

Overall, participants are expected to primarily experience a reduction in flow with study product use.

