11.1 Adverse Events

Menstrual bleeding and cramping/pain are recorded in a daily subject diary and not on the Adverse Events CRF. The subject daily diary has been designed to collect IUS and menstrual bleeding and cramping AEs following insertion of the study IUS. Menstrual bleeding or cramping/pain would only be entered onto the general AE CRF if:

- Bleeding or cramping/pain meet serious criteria; an SAE report would also have to be submitted (this exception is due to data system requirements)
- Bleeding or cramping/pain result in the IUS being removed (this exception is due to data system requirements)

- Bleeding or cramping/pain is not related to the IUS or a menstrual condition

All adverse event summaries will be restricted to treatment-emergent adverse events (TEAE), defined as AEs occurring during or after attempted IUS insertion and those pre-attempted IUS insertion existing medical conditions that worsened during the study up to the subject's last known IUS date of use or, for subjects who have discontinued, through the safety contact after the subject's last known IUS date of use. If an AE cannot be determined as treatment-emergent, it will be counted as such.

Verbatim terms on case report forms will be mapped to preferred terms and system organ classes using the Medical Dictionary for Regulatory Activities (MedDRA) dictionary. Each adverse event summary will be displayed by treatment group. Summaries that are displayed by system organ class and preferred terms will be ordered by descending order of incidence of system organ class and preferred term within each system organ class. Summaries of the following types will be presented:

- Overall subject summary of AEs, SAEs, and deaths
- Subject incidence of TEAEs and total number of unique TEAEs by MedDRA system organ class and preferred term.
- Subject incidence of TEAEs by MedDRA system organ class, preferred term, and highest severity. At each level of subject summarization a subject is classified according to the highest severity if the subject reported one or more events. AEs with missing severity will be considered severe for this summary

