11.6 Continuation, Expulsion, and Removal Rates

Cumulative rates of IUS continuation, expulsion, and safety-related removal at 1 month (Visit 6), 3 months (Visit 7) and 6 months (Visit 8) will be summarized and analyzed using Kaplan-Meier methods. Time to event will be calculated as the date of continuation/expulsion/removal minus the date of IUS insertion plus one. Subjects without a continuation/expulsion/removal will be censored at the last contact date (as described in [Section 5.4](#)) and failure time will be calculated as the last contact date minus the date of IUS insertion plus one. Subjects who report an expulsion that is not confirmed by the study site will be censored. The safety-related removal rates may also be summarized by MedDRA preferred term in the same manner. Expulsion rates including analysis of complete and partial expulsions in the Safety Population will also be summarized.

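### Protocol 7.11 codes some AE-driven IUS removals as no action, and the SAP plans no summary of all TEAEs leading to removal

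*Protocol*

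**What the plan says.** Protocol 7.11 sets the codes for the action taken with the IUS after an adverse event:

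- *None* is defined as "The IUS was not removed as result of the Adverse Event". Its sub-cases include a removal that coincided with the event but had another cause. The last of these is: "The subject wanting the IUS removed because of the AE despite the investigator stating the AE was not a reason".
- *Non-Safety Reasons* covers the case where "The IUS was removed for an Adverse Event even though the IUS could have remained in place", with no immediate risk of a serious complication.
- *Safety Reasons* applies when the IUS came out "because the subject was at immediate risk for a serious complication as a direct result of the AE".
- *Unknown* is for removal by another provider.

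Two capture rules bear on this. Protocol 7.6 says: "All AEs that result in permanent discontinuation of the investigational product must be reported", serious or not. Protocol 7.10.1, repeated in SAP 11.1, keeps IUS-related menstrual bleeding and cramping in the diary. Such an event goes on the general AE form only if it is serious or led to removal.

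On analysis, SAP 11.6 plans Kaplan-Meier estimates for "Cumulative rates of IUS continuation, expulsion, and safety-related removal", as does Protocol 9.9. SAP 11.1 lists its summaries, starting with "Overall subject summary of AEs, SAEs, and deaths". The others are by system organ class and preferred term, severity, relationship to the IUS, relationship to the procedure, and seriousness. SAP 7.1 tabulates the primary reason for discontinuation.

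**The concern.** Tolerability is a stated secondary objective (Protocol synopsis; SAP 2.2). In a single-arm study of a device that a woman can have removed whenever she chooses, removal because of an adverse event is the most direct measure of it.

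The last sub-case under *None* records the opposite of what happened: the event is why the IUS came out, and the field says it was not. Which code applies turns on whether the investigator agreed with the woman. Removals that escape *None* but lack immediate serious risk fall into a second code for which no removal rate is named. A reader of the report could see a low safety-related removal rate and take it as the rate of removal for side effects.

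The reasons for early exit also help in reading the efficacy result. A woman who leaves before the Cycle 3 collection has no treatment-phase MBL and drops out of the MITT population. The ITT analysis with baseline carried forward counts her, but only as a sensitivity analysis.

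**Working it through.** The plan states no figure on this point, so there is nothing to reproduce. The check sets the rules side by side and then gives an illustration of scale.

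**Step 1: one woman through the rules.** She has non-serious cramping attributed to the IUS and asks for removal because of it. The investigator says the cramping is no reason to remove. The IUS is removed at her request.

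- Under Protocol 7.10.1 the cramping goes on the general AE form, and the only qualifying reason is that it led to removal.
- Under Protocol 7.11 the action on that same record is *None*, meaning that it did not lead to removal.

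The record exists because of a fact that its action field denies.

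**Step 2: the codes against the planned outputs.**

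| Case | 7.11 code | Shown as a TEAE leading to removal | In the safety-related rate | In the continuation rate and reasons table |
|---|---|---|---|---|
| Woman cites AE, investigator disagrees | *None* | No such table | No* | Yes |
| Removed for AE, no immediate serious risk | *Non-Safety Reasons* | No such table | No* | Yes |
| Removed for AE, immediate serious risk | *Safety Reasons* | No such table | Yes* | Yes |

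*If safety-related in SAP 11.6 means the 7.11 code of similar name. Neither SAP 11.6 nor Protocol 9.9 says so.

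In all three cases the event itself is counted in the general TEAE tables. What no planned table shows is which events led to removal. SAP 11.6 allows an optional summary by preferred term, but only for safety-related removals.

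**Step 3: illustration of scale.** Inputs: about 100 women (Protocol 9.1), and Protocol 7.1.1, which reports of earlier trials: "Only 6% of women using the LNG 52 mg IUS for HMB in these trials discontinued for bleeding complaints". Assume that rate applies here.

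- Expected removals: 0.06 × 100 = 6.
- Exact 95% interval for k of n: lower limit = Beta quantile 0.025 with parameters (k, n − k + 1); upper limit = Beta quantile 0.975 with parameters (k + 1, n − k). For 6 of 100 this gives 2.2% to 12.6%.
- If none of the six carried immediate serious risk, the safety-related rate would be 0 of 100. Its upper limit is 1 − 0.025^(1/100) = 3.6%.
- Range: 3 of 100 gives 0.6% to 8.5%. At the other end, 15 of 100, Protocol 9.1's assumed limit on early discontinuation for all reasons together, gives 8.6% to 23.5%.

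The 6% covers bleeding complaints only and comes from pooled trials with results reported to one year, so the six-month figure could be lower. Pain or hormonal complaints would add to it, and the documents give no figure for them. It says nothing about how often an investigator disagrees with the woman, which is the only route to the *None* code.

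**The case against.** The strongest reply is that the information is collected and mostly reported. Every AE causing permanent discontinuation must be reported. All TEAEs are tabulated by term, severity and relationship. Protocol 9.3 counts removals, SAP 7.1 gives the primary reason for discontinuation, SAP 11.6 gives the continuation rate, and SAP 5.1 promises listings by subject. The *Non-Safety Reasons* code itself identifies AE-driven removals. This stands, and it rules out a reading that some may be tempted by: that the plan hides AE-driven discontinuation.

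Three other inferences also go too far.

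- That every removal requested because of an AE is coded *None*. The sub-case applies only where the investigator states that the AE was not a reason to remove.
- That the safety-related rate is known to cover only immediate-risk removals. That is the plausible reading, but the SAP does not define the term or cite 7.11.
- That the 6% measures the miscoding. It does not.

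It is also fair to say that investigators judge severity and causality throughout, and that with one arm there can be no differential coding between arms.

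The reply does not remove the contradiction in 7.11 or supply the missing link between event terms and removal. The reason categories behind SAP 7.1 and the fields of the IUS Discontinuation form are not shown in the documents. A *None* case might therefore be classed there as subject request, and the reasons table cannot be relied on to repair the code.

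**Conclusion.** The point holds in a limited form. One sub-case in Protocol 7.11 contradicts the definition it sits under and conflicts with Protocol 7.6 and 7.10.1. The SAP plans no summary of all TEAEs leading to IUS removal, and its one cause-specific removal rate for adverse events uses an undefined term. AE-driven removal would be partly miscoded and under-described in a study with tolerability as a secondary objective.

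The size cannot be fixed from the documents. On the assumption of 6 AE-driven removals in 100 women, none with immediate serious risk, and with safety-related read as the 7.11 code, the planned rate would show 0% against an any-AE removal rate of 6%. The frequency of the *None* case is unknown. The primary endpoint, the success rule and the sample size are unaffected. This should be corrected, but it is a matter of coding and reporting.

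**What to change.** - **Protocol 7.11 and the form completion guide:** take the subject-request case out of *None*. Code any removal for which the woman or the investigator gives an AE as the reason as removal due to that AE. Keep the investigator's opinion and the safety/non-safety split as separate fields.
- **SAP 11.6:** state which 7.11 codes count as safety-related.
- **SAP 11.1:** add a table of TEAEs leading to IUS removal by system organ class and preferred term. A Kaplan-Meier estimate of removal for any AE is optional; with about 100 women the table may be enough.

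The additions should be made before database lock, because SAP 5.1 treats analyses performed after it as post hoc.

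The cost is a wording change, a review of removal records already coded *None*, and one table. That review depends on the woman's stated reason having been captured, which the documents do not confirm. The stated AE-discontinuation rate would be higher. Nothing here alters when or whether an IUS is removed.
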